Using the Zoom App, participants will be invited to watch the Baduanjin mind-body exercise demonstration videos which explains how to perform the exercise movements where the instructor will explain and demonstrate the eight movements and natural breathing methods with the participants. This is done before commencing the first exercise session in the program.

In addition to self-guided practice, the participants will be asked to join in a coached Zoom exercise program with an instructor, either in the morning or afternoon or both sessions at their own choice throughout the intervention period (8 weeks). Participants will be requested to practice Baduanjin mind-body exercise at least 2 sessions per day, 6 days per week with each session lasting about 15 mins for 8 weeks. Missed sessions will not be considered as a protocol deviation.

The Baduanjin mind-body exercise sessions via Zoom are instructed by members of the research team who have at least two years' experience in the practice of Baduanjin mind-body exercise. If participants miss out on any Zoom sessions, they can watch the demonstration video as a reference. Participants will be asked to record their daily Baduanjin mind-body exercise schedule in the Exercise Logbook. Recording this in the Exercise Logbook will take approximately 2 minutes each session. This will happen twice daily, 6 times per week for 8 weeks. Weekly telephone calls will be performed by a research assistant to see how the participants are progressing and engaging with the Baduanjin mind-body exercise program. The weekly phone calls will also discuss any unexpected side effects or adverse events that might be related to the exercise.

Finally, participants are asked to complete two (2) questionnaires at baseline (week 0) as part of the study intake process, and again at the end of week 4 and week 8 of the exercise program. These questionnaires are the brief fatigue inventory (BFI) and the PROMIS-29v2.0. The BFI measures fatigue. The PROMIS-29v2.0 is a patient reported outcome measure used by health services in NSW. Together, these will take 5-10 minutes to complete online and can be accessed using secure links that will be emailed to participants.

There is also the *Credibility and Expectancy Questionnaire* (CEQ) which has four questions and takes one minute to complete. Two questions are completed before entry into the study (week 0), and two at the completion of the Baduanjin mind-body exercise program (week 9).

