One week after completing the Baduanjin mind-body exercise program (in week 9), a study team member will contact participants by phone for a final time. This is to check on the participant and see if there have any reports or adverse experiences. Participants will also be asked to complete for the final time the BFI and the PROMIS-29v2.0, along with the final two questions from the CEQ.

The timeline below illustrates the weeks required to meet via phone call or video call from the start of the trial through to completion of the trial.

[figure not shown]

Figure 2: Intervention group and control group study flow

Baduanjin mind-body exercise includes three phases: warm-up, exercise, and cool-down which together, consist of the intervention in this study.

During the warm-up and cool-down phases, the participants will perform deep breathing and stretching exercises to improve range of motion in their joints and flexibility and reduce possible muscle and joint soreness.

During the exercise phase, the participants will perform eight sets of movements led by the Baduanjin mind-body exercise video and/or instructor via Zoom. Each set of movements are classically described and shown with an image approximating the completed movement in the *Baduanjin Mind-Body Exercise Instruction Handbook*. All movements require a mindful mental focus to coordinate sequenced body movements with breathing.

Wait list control group

From week 0 to week 9 (10 weeks in total), participants will receive their usual care/medications and undergo no Baduanjin mind-body exercise intervention. Participants in the waitlist control group also maintain their lifestyle without modifications to usual daily care routines. Participants will be asked to complete the BFI and the PROMIS-29v2.0 questionnaires to monitor changes in their cancer-related fatigue to compare changes with the intervention group. This will happen upon enrolment into the study (week 0 - baseline), and at week 4, week 8 and again at week 9.

Participants in the waitlist control will be offered entry into the Baduanjin mind-body exercise program at completion of their waitlist control period. Entry will be as a non-study participant which means access to the exercise program but without any further need to complete questionnaires. This is voluntary and no longer as part of the study.

The summary of the total approximate time participants dedicate to the study is noted below:

Intervention group (approx. 28 hours)

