The *Credibility and Expectancy Questionnaire* has been modified to assess participants perspectives on the credibility of the Baduanjin mind-body exercise program for their fatigue [32]. There are four (4) questions and takes 1 minute to complete. Questions 1 & 2 are completed before randomisation about participants expectations, and questions 3 & 4 after the final Baduanjin mind-body exercise session on the credibility of their experience [33]. Each question is measured on a Likert scale of 1-9 where 9 is the most credible.

Exercise Logbook

Participants in the intervention group will be asked to record their daily Baduanjin mind-body exercise schedule in a logbook for the 8 weeks of their exercise. This takes approximately 2 minutes each day or 10 minutes a week in total. The logbook helps understand any relationship between frequency of exercise and changes in CRF scores. It additionally assists with determining feasibility with adherence rates.

Final Feedback Form (Week 9)

Participants in the intervention group will be contacted by a member of the research team to thank them for their participation and inform them the final feedback form will be the last data collection. The research team member will check the completion of final outcome

measures and ask if participants would like a copy of the study report of findings. The participant will also be asked for further feedback on the participants experiences and future changes to assist with participation and completion of the program.

Adverse Events Reporting and Management

There are weekly telephone calls with a member of the research team to check on participants engagement with the Baduanjin mind-body exercise program and discuss any exercise related expected and unexpected side effects. If present, these are reported using the Adverse Events Form. The Principal Investigator is responsible for assessing any event as meeting the adverse event criteria threshold. Participants can report any side effects of concern daily with the exercise instructors (who are also registered health care practitioners), and these will also be reported in the Adverse Events Form for the Principal Investigator to investigate and decide.

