Each intervention group participant will receive an Exercise Logbook for reporting side effects of concern related to the Baduanjin mind-body exercise program. All Serious Adverse Events (SAEs) occurring between consent and the last visit for the study are recorded in detail in the Adverse Events Form by the member of the research team who received the original report, and who also informs the Principal Investigator. All AEs that occur between the first intervention and the last intervention for the study must be recorded in detail. In case of an AE/SAE, the Principal Investigator will initiate contact with appropriate members of the participant's health care team, or as according to their health care judgement given the nature of the AE/SAE. If necessary, participants will be withdrawn from the study. Participants with SAE/AEs present at the last intervention will be followed up until resolution of the event.

The SWSHLD Ethics Committee will be notified of any AE/SEA. Regular meetings will be scheduled by the Principal Investigator to discuss the AE with hospital clinicians. Participants will be provided a 24-hour contact number for any urgent matters or concerns. The severity, expectedness and causal relationship with the intervention will be assessed for every AE reported. The number and severity of AE, as recorded on an Adverse Events Form, will be reported in adherence to the requirements of the National Health and Medical Research Council for Clinical Trials Adverse Event Reporting.

Endpoints

Key feasibility endpoints are recruitment rates, and the participation and completion of the study interventions (from Logbook data) within the stated study periods. For feasibility and contributing to the design of a larger clinical trial, the primary outcome measure endpoint

will also include the effect of Baduanjin mind-body exercise on changes of fatigue as measured by the BFI score at baseline (week 0), at 4 weeks (mid-point), 8 weeks (final week) and 9 weeks (1 week follow-up) [29] (Additional secondary outcome measure endpoints will be the PROMIS-29v2.0 [28] and reported adverse events at baseline (week 0), 4 weeks, 8 weeks and 9 weeks (1 week follow-up) (Appendix 1. & Figure 1.) Participant's credibility and expectation ratings are compared prior to study group randomisation with their credibility scores on completing the Baduanjin mind-body exercise program.

Data analysis

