12. APPENDICES

1. Study Assessment Time-points

		Week 0 (Baseline)	Week 1	Week 2	Week 3	Week 4	Week 5	Week 6	Week 7	Week 8	Week 9 (Follow-up)
PIS and Consent	X										
Information phone call	X										
Screening (inclusion/exclusion)	X										
Consent & Enrolment		X									
Randomisation		X									
Information pack		I									
Baduanjin Zoom		I	I	I	I	I	I	I	I	I	
AE Assessment			I	I	I	I	I	I	I	I	I
Telephone Check-in		I & W	I	I	I	I & W	I	I	I	I & W	I & W
BFI	X	X				X				X	X
PROMIS-29 V2.0		X				X				X	X
CEQ (questions 1,2)		X				X				X	X
CEQ (questions 3, 4)		X									X

X = everyone

I = Baduanjin Intervention group

W = Waitlist control group

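### The protocol contradicts itself on the Credibility and Expectancy Questionnaire: text and Appendix 1 collect different items at different times from different people, and neither supports the stated before/after comparison

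*Protocol*

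**What the plan says.** The questionnaire (CEQ) is secondary outcome (d) in protocol Section 10, which sets perceptions before randomisation against perceptions after the programme. The Summary (Section 1) also presents it as a rating made before and after.

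- **Section 10, CEQ paragraph.** The first pair of items comes at baseline: "Questions 1 & 2 are completed before randomisation about participants expectations". The second pair is placed at the end of the programme: "questions 3 & 4 after the final Baduanjin mind-body exercise session on the credibility of their experience". On scoring: "Each question is measured on a Likert scale of 1-9 where 9 is the most credible".
- **Section 5.8, under the intervention-group heading.** "Two questions are completed before entry into the study (week 0), and two at the completion of the Baduanjin mind-body exercise program (week 9"). The week 9 contact repeats this: the BFI and PROMIS-29 are completed "along with the final two questions from the CEQ".
- **Section 5.8, waitlist paragraph.** It names only the BFI and PROMIS-29 and does not mention the CEQ. It states that this group receives no Baduanjin from week 0 to week 9.
- **Section 10, Endpoints.** Participants' "credibility and expectation ratings are compared prior to study group randomisation with their credibility scores on completing the" programme.
- **Appendix 1.** The row for questions 1 and 2 carries an X at weeks 0, 4, 8 and 9. The row for questions 3 and 4 carries an X at weeks 0 and 9. The key defines X as everyone.

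**The concern.** Three statements about one outcome do not fit together. The text collects two items before and two other items after. The Endpoints paragraph compares before with after, and assumes that a credibility rating exists before randomisation. Appendix 1 collects all four items before and after, but in doing so puts questions about the experience to people who have had none.

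Staff who build the forms cannot satisfy both schedules. Under the text, a before/after difference would set an expectation item against an experience item, and that is not a change in one perception. Under Appendix 1, the week 0 answers to questions 3 and 4, and the waitlist answers at week 9, have no experience behind them. Baseline answers that are not collected before randomisation cannot be recovered afterwards, so the choice has to be made before data collection and cannot wait for the analysis.

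**Working it through.** No power or sample size figure bears on this point. The check sets the schedules side by side and counts the responses that each implies.

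**Inputs.** 40 participants, 20 per arm (Section 1); four CEQ items in two pairs (Section 10); timings from Sections 5.8 and 10 and from Appendix 1; no dropout assumed.

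**Is the Appendix 1 grid read correctly?** Read with the same columns, the PROMIS-29 row gives weeks 0, 4, 8 and 9, and so does the BFI row apart from its extra screening mark. This agrees with the times in Section 5.8. The CEQ marks are therefore unlikely to have been shifted when the table was extracted.

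**Schedules compared.**

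| | Text (5.8 and 10) | Appendix 1 |
|---|---|---|
| Questions 1 and 2 | once, before randomisation | weeks 0, 4, 8, 9, everyone |
| Questions 3 and 4 | once, after the programme | weeks 0 and 9, everyone |
| Items asked both before and after | 0 of 4 | 4 of 4 |
| Credibility rating before randomisation | none | questions 3 and 4, before any exercise |

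**Item responses = participants × items × times.**

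- Text, taking questions 1 and 2 in everyone (allocation is not yet known) and questions 3 and 4 in the intervention arm: 40 × 2 × 1 + 20 × 2 × 1 = 80 + 40 = 120.
- Appendix 1: 40 × 2 × 4 + 40 × 2 × 2 = 320 + 160 = 480.
- Excess: 480 − 120 = 360. Of these, 40 × 2 × 3 = 240 are repeats of questions 1 and 2 at weeks 4, 8 and 9. A further 40 × 2 = 80 are questions 3 and 4 at week 0, and 20 × 2 = 40 are questions 3 and 4 at week 9 in the waitlist arm (240 + 80 + 40 = 360).

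Of the 160 responses to questions 3 and 4 under Appendix 1, 80 + 40 = 120 come from people who have not done the programme. The other 40 are the intervention arm at week 9, the only ones that the CEQ paragraph describes.

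**Does either schedule support the Endpoints sentence?** The text does not: it supplies expectation before and credibility after, and no credibility before. Appendix 1 supplies a week 0 answer to questions 3 and 4, but by Section 10's own description those items rate an experience that has not yet happened.

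**The case against.** The strongest reply is that this is a slip in a table. Sections 5.8 and 10 agree with each other on two items before and two after. The CEQ is described under the intervention-group heading, and the waitlist paragraph leaves it out. The row for questions 1 and 2 has the same marks from week 0 onward as the PROMIS-29 row, which would fit a copying error. That is plausible but not shown. It would also leave the Endpoints sentence unrepaired, because that sentence needs a baseline credibility rating which the text does not collect.

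Several stronger readings are tempting, and the protocol does not support them:

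- **That the plan subtracts one construct from another and so yields a meaningless number.** The protocol says that the ratings are compared; it specifies no difference score. Outcomes (a) and (b) are worded as changes, but (d) is not. Expectation set beside experienced credibility on the shared 1 to 9 scale can be interpreted. Only a difference read as a change in perception cannot.
- **That both harms occur together.** They are alternatives. Different questions before and after follows from the text; unexposed people rating an experience follows from Appendix 1.
- **That both item pairs go to the wrong people.** Questions 1 and 2 before randomisation properly apply to everyone. Waitlist participants are later offered the programme, so they could still answer them after week 0. The objection about who is asked concerns questions 3 and 4.
- **That the CEQ is the trial's only evidence on acceptability.** Section 1 assesses feasibility and acceptability through recruitment, retention and adherence, and the week 9 feedback form also asks about experiences.

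The item wording is not in the protocol, so the difference in content between the two pairs rests on the description in Section 10.

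**Conclusion.** The contradiction stands. The text and Appendix 1 prescribe different data for a named secondary outcome: 120 against 480 item responses with 40 participants and no dropout, and none against all four items asked both before and after. Neither schedule as written supports a sound before/after comparison, and the Endpoints paragraph presupposes a baseline credibility rating that the CEQ paragraph does not provide.

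The conclusion assumes that the Section 10 description of the items is accurate, that X in Appendix 1 means both arms as its key states, and that the text intends questions 1 and 2 for everyone and questions 3 and 4 for the intervention arm. The consequence is limited. This is a descriptive secondary outcome of a feasibility trial, and neither the sample size nor the recruitment, retention and adherence rates depend on it. It should be corrected because the correction is cheap and a missed baseline rating cannot be collected later.

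**What to change.** Reconcile Sections 5.8 and 10 with Appendix 1, and state for each pair of items the time and the arm:

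1. Questions 1 and 2 at week 0, before randomisation, in all participants. Add this to the waitlist paragraph of Section 5.8, and remove the later marks from Appendix 1.
2. Questions 3 and 4 at week 9, in the intervention arm only. In Appendix 1, remove the week 0 mark and change the week 9 mark from X to I.
3. Reword the Endpoints paragraph, and align secondary outcome (d) and the Summary, so that expectancy and post-programme credibility are reported separately, side by side and descriptively, and not as a before/after change.

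If a before/after change is wanted, ask identically worded items at both times in the intervention arm, after checking that the wording still makes sense at week 9. Simply repeating the expectation items once the programme is over is a debatable choice, so this is an option and not part of the minimum correction.

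The cost is wording and a form setting. The minimum correction adds no measurement beyond what the text already plans. The option adds a few items to a questionnaire that the protocol puts at one minute.

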6.3 Confidentiality and Privacy

Data collection and management

All study data collected will be recorded in the Case Report Forms and other templates prepared for this study. Socio-demographic information, medical history, any occurrence of adverse events and intervention outcomes during the study will be collected and recorded on paper or in electronic files.

All electronic data will be entered and managed using the Research Electronic Data Capture (REDCap) management system, and/or with Microsoft (MS) Excel spreadsheets and MS Word files with compatible file formats for SPSS (V 24.0; IBM Corp; Armonk, NY, USA).

Each member of the research team has responsibility for the accuracy, authenticity, collection and reporting of all clinical and safety data, or any other data on collection forms and to enter data as it is reported (such as during telephone calls) or as received (returned outcome measures). All completed forms must be signed by the research team member collecting the information or by an authorised team member to attest that the data contained on the study collection forms is true. The Principal Investigator or nominated research team member will audit the records weekly to ensure compliance with the study protocol.

Confidentiality and Privacy

Any information obtained in connection with this study that can identify a participant will remain confidential. Identifying information is also kept separate from other information provided on other study forms. Participants will be randomly allocated a study identification code. Consequently, the participants code will be appended to all data collection forms relating to their participation in this study.

The coding key is held separate from participant's identifiable and de-identified study information and documentation, to assist in maintaining data de-identification. The coding key is locked in a password-protected cloud partition in the WSU's computer systems so it cannot be used to decode participant's information. A hardcopy of the coding key is also held separately in a locked file in the Chinese Medicine Centre (CMC) (Level 3, School of Health Sciences, Western Sydney University (WSU), Campbelltown Campus) accessible to the study team. Only the members of the research team have access to the

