Data are transcribed into an excel spreadsheet and checked for accuracy. Data will be cleaned using frequency counts and logic checks. At the completion of cleaning the final data set will be locked with any further errors addressed as study limitations. Analyses of the endpoints will follow the Intent-to-Treat (all participants as per randomisation) and per-protocol (participants adhering to the protocol). These analyses will include, as appropriate, participant demographic (co-variates) and Baduanjin mind-body exercise participatory frequency data. Participant demographics and data will be summarised at baseline using sample means and proportions with corresponding 95% confidence intervals. We will explore and report confounders in the modelling.

To our knowledge, this will be the first study evaluating the feasibility and effects of Baduanjin mind-body exercise on cancer-related fatigue using a remote delivery method. Data will therefore help calculate an effect size for predicting power in a larger future study. This includes using these data to formulate study hypotheses. As such, data will be transformed to ensure approximate normal distributions.

All data will be entered and managed using the Research Electronic Data Capture (REDCap) management system and all analyses performed using SPSS (V 24.0; IBM Corp; Armonk, NY, USA) or descriptive analyses and data sorting with Microsoft Excel.

Publication

The results of this study will be published and/or presented in journal articles, conference posters, seminars and presentations. We will use de-identified and aggregated data. In any publication and/or presentation, it will be impossible to identify participants.

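### Errors found after data lock are to be listed as limitations, not corrected, even where source records would settle them; the file to be locked is also not clearly named

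*Protocol*

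**What the plan says.** The Data analysis part of Protocol section 10 gives the sequence. Data enter a spreadsheet and are checked: "Data are transcribed into an excel spreadsheet and checked for accuracy". Cleaning follows: "Data will be cleaned using frequency counts and logic checks". Then comes the lock and the rule for anything found later: "At the completion of cleaning the final data set will be locked with any further errors addressed as study limitations".

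The data system is described in three ways. The first is the Excel transcription just quoted. The second, later in the same part of section 10, is "All data will be entered and managed using the Research Electronic Data Capture (REDCap) management system and all analyses performed using SPSS". The third, in section 6.3, is REDCap "and/or with Microsoft (MS) Excel spreadsheets and MS Word files with compatible file formats for SPSS".

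For the BFI and PROMIS-29, section 5.8 says that "these will take 5-10 minutes to complete online and can be accessed using secure links that will be emailed to participants". Section 6.3 allows other data, such as medical history and adverse events, to be on paper or electronic. Section 6.4 keeps both kinds of record for 5 years and refers to a Research Data Management Plan, which is not among the documents at hand.

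**The concern.** Locking a data set protects the analysis from informal changes made after results are seen. It does not require a known, verifiable error to stay in. The usual safeguard is a controlled unlock with a record of what changed and why. Here the protocol names only one outcome for a late error, a note among the limitations, and does not separate errors that source records can resolve from those they cannot.

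At stake are the primary feasibility rates, which have small denominators, and the BFI effect estimate, which section 10 intends to use in planning a larger trial. A reader told that a rate contains an error, but not given the corrected rate, cannot use it properly.

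A second, smaller matter is that a lock rule needs a definite object. With three descriptions of where the data live, it is not certain which file the lock applies to.

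**Working it through.** **1. Reading the rule.** The sentence covers all further errors without exception. No other part of the protocol describes correction after lock. Section 6.4 retains source records for 5 years, so for many late errors the true value could be looked up. Taken together, a verifiable wrong value would be disclosed and left in place.

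**2. Size of one uncorrected error.** The protocol gives no expected error rate, so what follows is the effect of a single error and not its likelihood.

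Inputs:
- 40 participants, 20 per arm (sections 1 and 5.3).
- 15% attrition (section 5.3): 20 × 0.85 = 17 left per arm.
- Adherence is divided by those allocated to the intervention, planned 20; retention is divided by those enrolled, planned 40 (section 10).
- The BFI global score is the mean of nine items (section 10). Items are taken to run from 0 to 10, as section 5.4 describes for the screening item, so one item can be wrong by at most 10.

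Results:
- Adherence, one participant misclassified: 1/20 = 0.05, or 5 percentage points.
- Retention, one participant misclassified: 1/40 = 0.025, or 2.5 percentage points.
- BFI, one item wrong by the full range: 10/9 = 1.11 on that participant's score. On the arm mean this is 1.11/20 = 0.056 with 20 participants, or 1.11/17 = 0.065 with 17.
- BFI, one item keyed 10 instead of 1: (10 − 1)/9 = 1.0 on the participant's score, and 1.0/20 = 0.05 on the arm mean.

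The last example is a permitted value, so a frequency count or range check would generally not flag it. Only a comparison with source would.

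**3. Which file is locked.** The statements set side by side:
- Section 10, opening of Data analysis: transcription into Excel, then cleaning, then lock.
- Section 10, end of Data analysis: REDCap for all data, with SPSS for analysis and Excel for descriptive work and sorting.
- Section 6.3: REDCap, Excel and Word as alternatives or in combination.

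These can be partly reconciled, for instance as REDCap capture with an Excel working file. The text does not say so, and it does not state which file is final.

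**The case against.** **The detail may sit elsewhere.** Unlock procedures and entry checks normally belong in a data management plan, and one is referred to. That would answer a complaint that the protocol is silent, but the protocol is not silent: it states an outcome for late errors. If the other plan allows correction, the two documents disagree and this sentence still needs changing. The objection does stand for most of the operational detail on data systems, where the protocol need only make clear which file is final.

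**There are controls before lock.** Section 10 includes an accuracy check before cleaning. Section 6.3 has forms signed as true and a weekly audit of records, though that audit is aimed at protocol compliance. These make a late error less likely. They do not change what happens to one that is found.

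**Stronger readings that the documents do not support:**
- A reader might infer that the trial will publish figures it knows to be wrong. That requires an error to surface after lock, and the protocol commits to disclosing it. Nothing is concealed, and correction is not expressly prohibited; it is simply given no route.
- A reader might put the possible shift in a BFI arm mean at 10/20 = 0.5, or 10/17 = 0.59. That needs all nine items for one participant to be wrong from one end of the scale to the other. A single item gives about one ninth of that.
- A reader might infer that online answers are to be retyped by hand into Excel. Online completion is documented only for the BFI and PROMIS-29, the platform behind the links is not named, and data on paper must be transcribed in any case.

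**Conclusion.** The point holds as a minor one. As written, the rule leaves a verifiable error in the analysis and reports it as a limitation. One such error would shift adherence by 5 percentage points or retention by 2.5, and a single mis-keyed BFI item would shift an arm mean by at most about 0.06. The feasibility rates are therefore the more exposed results.

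This rests on the plain reading of the sentence, on full enrolment of 40 split equally, on a 0 to 10 range for BFI items, and on the condition that an error is found after lock and can be resolved from source. How often that would happen cannot be estimated from the protocol. The descriptions of the data system support one further request only: say which file is locked and analysed.

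**What to change.** In the Data analysis part of section 10, replace the sentence on locking with: *An error found after lock that can be verified against source is corrected by a documented unlock, correction and relock; affected analyses are rerun and the change is listed. Only errors that cannot be resolved from source are reported as limitations.*

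Reconcile section 6.3 with the two statements in section 10 by naming the one file that is locked and analysed. State that online BFI and PROMIS-29 answers are exported into it and not retyped.

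The cost is a wording change, an unlock log, and possibly a rerun of an analysis. Design, visits and participant burden are unaffected. The change should be made before lock.
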